#### 1. ADMINISTRATIVE INFORMATION

**Title:** A feasibility study of Prehospital Optimal Shock Energy for Defibrillation (POSED)

**ISRCTN Trial registration number**: 16327029

SAP Version: 0.2, dated 24 June 2022

Protocol Version: 3.0, dated 10 November 2021

#### **SAP** revisions:

Version no.	Changes	Rationale for changes	Timing of change w.r.t. analyses

#### 2. INTRODUCTION

## 2.1 Background and rationale

Cardiac arrest, the cessation of the pumping action of the heart, is one of the primary causes of premature death across the world. (1) One fifth of patients sustaining a cardiac arrest in the out-of-hospital environment displays a shockable heart rhythm, i.e. one that may be treated with defibrillation. (2) . There is currently no clear consensus on the optimal shock energy for delivery by a defibrillator. European Resuscitation Council (ERC) guidelines advising both to treat with an initial energy of at least 150J for biphasic waveforms, escalating after a failed shock if the defibrillator is capable, and to base shock energy on manufacturers' guidance. (3) There is an urgent need for a large-scale randomised controlled trial to identify optimal shock energy for first and subsequent shocks. POSED is a stand-alone feasibility study addressing key unknowns that would inform a main trial. The main research question is:

Is it feasible to conduct a randomised, pragmatic clinical effectiveness trial in UK ambulance services to identify the optimal energy for defibrillation?

### 2.2 Objectives

#### **Primary Objective**

• To establish whether it is feasible to conduct a large-scale definitive trial by establishing the number of eligible patients and the number recruited.

## **Secondary Objectives**

- To measure the rate of adherence to the allocated treatment
- Identify the best outcome measures in terms of ease and reliability of recording by reviewing data completeness.
- Explore what affects treatment adherence and data completeness by eliciting the views and experiences of paramedics via focus groups.

#### 3. STUDY METHODS

## 3.1 Trial design

POSED is a single-centre, cluster-randomised multi-arm study. Defibrillators will be randomised to deliver one of three shock strategies:

Group	First shock	Second shock	Subsequent shocks	Strategy
1	120	150	200	Escalating
2	150	200	200	Escalating
3	200	200	200	Fixed

These three shock strategies represent current standard of care in UK Ambulance Services.

This feasibility study aims to recruit 90 patients, ideally 30 in each arm.

#### 3.2 Randomisation

POSED is a cluster randomised study and the unit of randomisation is the defibrillator. Defibrillators will be allocated to one of the three treatment groups in a 1: 1: 1 ratio using simple randomisation. The randomisation will be stratified by ambulance station and by vehicle type (ambulance/response car/team leader vehicle).

#### 3.3 Sample size

This feasibility study aims to recruit 90 patients, ideally 30 in each arm. It is popularly believed that a sample size should be at least 30, based on the central limit theorem whereby as a population becomes large it achieves an approximately normal distribution. (4) Although these is no statistical proof that 30 is a 'large' number in this context, my sample size of 30 in each treatment arm will be sufficiently large to inform discussion around secondary outcomes whilst allowing for missing data and loss to follow up.

#### 3.4 Framework

This is a feasibility study and as such is not testing statistical hypotheses.

#### 3.5 Blinding

This is an open-label study. It is not possible to blind ambulance staff to treatment allocation as they will see the shock energy when they charge the defibrillator. Patients and hospital staff will be blind to the treatment allocation. Those assessing outcomes at discharge/30 days will be blind to allocation although those assessing short term outcomes (cardiac electrical outcomes) will not be blind as the data will be taken from defibrillator data downloads which contain details of the shock energy delivered (the intervention).

## 3.6 Statistical interim analyses and stopping guidance

As this is a feasibility study there will be no interim analyses. The study will end when all participants have completed their 30 day follow-up or after 24 months of patient recruitment, whichever is sooner.

The study will be stopped prematurely if:

- Mandated by the Ethics Committee
- Following recommendations from the Study Oversight Committee (SOC)
- Funding for the study ceases

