## 3.7 Timing of outcome assessments

	Cardiac arrest	Hospital	Day 30
Inclusion/exclusion criteria	✓	X	Х
Cardiac arrest data	✓	х	х
Patient identifiers	✓	✓	Х

			THE UNIVER
Adverse event reporting	✓	✓	х
National data opt- out check	,	(	х
Survival checks	√	√	х
Survival status	√	√	√
Hospital stay data	X	√	Х
Notification of enrolment and invitation to take part in follow up	х	√	х
Informed consent	Х	√	х
Neurological outcome (mRS)	x	x	✓

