#### **6.1.2 Secondary outcomes**

- Treatment adherence rate. This will be assessed in terms of how many patients
  received the allocated first shock energy and, where more than one shock was
  delivered, how many received the correct subsequent shock energies. These will be
  reported as proportions for each treatment arm and overall.
- Data completeness of clinical outcomes below:
  - Neurologically intact survival at 30 days (mRS score)
  - Return Of Organised Rhythm capable of sustaining a pulse (ROOR) 2
     min post shock
  - Resulting rhythm (VF/pVT/PEA/asystole) 2 min post shock
  - Re-arrest rate (re-fibrillation)
  - Survived event (return of spontaneous circulation (ROSC) at hospital handover)
  - Survived to hospital discharge

These will be reported in terms of the proportion of patients for whom each of these outcomes was collected.

- Data completeness of process outcomes below:
  - Quality of CPR (chest compression rate, chest compression depth, chest compression fraction, pre-shock pause, post-shock pause)
  - Number of shocks
  - Advanced airway applied (% advanced airway applied and % supraglottic airway or endotracheal tube)
  - Intravenous medicines administered (% cases where medicines administered and % adrenaline, amiodarone)

Transported to hospital (% transported)

These will be reported in terms of the proportion of patients for whom each of these outcomes was collected.

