## 6.3 Missing data

All reasonable attempts will be made to prevent missing data. Since this is a feasibility study, only the proportion of missing data will be reported. No imputation or other techniques will be employed to minimise the impact of missing data.

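### The end-of-study rule can close the study before late-enrolled survivors reach day 30, so a few 30-day survival and mRS results would be missing because of the rule itself

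*SAP*

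**What the plan says.** SAP section 3.6 sets the end of the study: "The study will end when all participants have completed their 30 day follow-up or after 24 months of patient recruitment, whichever is sooner". One limb concerns follow-up and the other concerns recruitment, and the earlier of the two ends the study.

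The table in section 3.7 marks survival status at day 30, and it marks the mRS at day 30 only. Section 6.1.2 puts "Neurologically intact survival at 30 days (mRS score") first among the clinical outcomes whose completeness is a secondary outcome, and gives the measure: "These will be reported in terms of the proportion of patients for whom each of these outcomes was collected". Section 2.2 makes the review of data completeness the means of choosing outcome measures for a main trial.

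On missing data, section 6.3 says "All reasonable attempts will be made to prevent missing data" and also "No imputation or other techniques will be employed to minimise the impact of missing data". In section 7, the survival and neurological outcome tables each have a single undivided row for missing values. The withdrawals table has lines for withdrawal and loss to follow-up, but none for patients cut off by study closure.

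On size, section 3.3 says: "This feasibility study aims to recruit 90 patients, ideally 30 in each arm".

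**The concern.** The sentence uses a limit on recruitment as a limit on the study. If patients are still being enrolled close to month 24, the study closes before the most recent of them can reach day 30. No other section of the SAP stops enrolment 30 days early, carries follow-up past closure, or separates patients cut off by closure from other missing values.

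In most trials this would be a minor loss of data. Here the completeness of 30-day mRS is itself something the study reports, and it is meant to show whether that outcome can be collected in a main trial. Missing values made by the calendar would be counted with those that reflect real difficulty in collection. The 24-month limb applies when recruitment is slow, and slow recruitment is one of the things a feasibility study exists to detect.

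**Working it through.** **Order of the two limbs.** Suppose a patient is enrolled at day *t* of recruitment and the recruitment limb falls at day *T* (24 months). The patient's day 30 is at *t* + 30. If *t* > *T* − 30, then *t* + 30 > *T*, so follow-up is unfinished when the recruitment limb is reached. Whenever anyone is enrolled in the last 30 days before month 24, the recruitment limb is therefore the sooner one.

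**Who loses data.** A patient who dies before closure has a known 30-day result: dead, mRS 6, which is a category in the section 7 template. Only late-enrolled patients still alive at closure lose the day-30 items.

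**Inputs from the SAP.** Three arms of 30 (sections 3.1 and 3.3), giving 3 × 30 = 90, which agrees with the stated total. Recruitment limit of 24 months and follow-up of 30 days (section 3.6). The SAP states no figure for patients with truncated follow-up, so there is nothing further to reproduce.

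**Assumptions.** The SAP gives no accrual pattern, so even and linearly rising accrual are both shown. The share alive at closure among late enrollees is taken as 5% to 50%. 24 months = 24 × 365.25/12 = 730.5 days.

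**Enrolled in the last 30 days**

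- Even accrual, share = 30/730.5 = 4.1%:
  - 90 patients: 90 × 0.0411 = 3.7
  - 60 patients: 60 × 0.0411 = 2.5
  - 45 patients: 45 × 0.0411 = 1.8
- Linearly rising accrual, share = 1 − (700.5/730.5)² = 8.0%:
  - 90 patients: 90 × 0.0804 = 7.2

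With 90 patients and even accrual, the chance that at least one is enrolled in the last 30 days is 1 − (1 − 0.0411)^90 = 0.98.

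**Alive at closure, and so losing day-30 data (N = 90)**

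| Accrual | Enrolled late | 5% alive | 50% alive |
|---|---|---|---|
| Even | 3.7 | 3.7 × 0.05 = 0.2 | 3.7 × 0.50 = 1.8 |
| Rising | 7.2 | 7.2 × 0.05 = 0.4 | 7.2 × 0.50 = 3.6 |

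(Products are taken before rounding.)

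**Effect on the reported completeness.** The measure is a proportion of patients. With 90 patients the loss is 0.2/90 = 0.2 to 1.8/90 = 2.0 percentage points under even accrual, and 0.4/90 = 0.4 to 3.6/90 = 4.0 points under rising accrual. For scale, at an assumed completeness of 80% the 95% confidence half-width with 90 patients is 1.96 × √(0.8 × 0.2/90) = 0.083, about 8 points.

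**With recruitment and follow-up separated.** If the study ends only when the last recruited patient has completed 30 days, the rule truncates no one.

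**The case against.** The strongest reply is that the loss is conditional and small. If 90 patients are recruited and followed up before month 24, the rule costs nothing, and the SAP gives no accrual rate from which to say that the 24-month limb will apply. If it applies because recruitment is slow, fewer than 90 patients have been enrolled and the count falls with them. The shift in completeness is well inside its sampling uncertainty. The primary outcome, the proportion of eligible patients randomised, is not touched, and section 3.4 rules out hypothesis testing. End-of-study rules commonly sit in the protocol, which is not at hand, and the SAP sentence may be a loose paraphrase of it. All of this stands. It limits the size of the point but does not repair the sentence.

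Three stronger readings are tempting, and the document does not support them.

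- A reader might infer that everyone enrolled in the last month loses 30-day outcomes. That is not so, because deaths before closure are already known outcomes. The 3.7 counts late enrolments, not lost results.
- A reader might infer that the rule contradicts section 6.3. That section promises reasonable attempts to prevent missing data. A fixed closing date is at odds with that aim but does not contradict it.
- A reader might infer that the follow-up limb is met whenever nobody happens to be in follow-up, however few have been recruited. Sections 3.1 and 3.3 both state the aim of 90, and the natural meaning of all participants is the planned sample.

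**Conclusion.** The point holds as a defect in the wording of section 3.6, with a small and conditional effect. If recruitment runs to month 24, patients enrolled in the last 30 days and still alive at closure lose their day-30 survival status and mRS because of the rule. Fewer than two patients are expected to be affected under even accrual of 90, and fewer than four under rising accrual. Both figures rest on assumed accrual patterns and an assumed 5% to 50% alive.

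It is still worth correcting. The missing values fall on survivors, the patients whose mRS has to be collected by follow-up, and they enter a completeness figure that is meant to describe collectability. Whether follow-up would really be cut short in the conduct of the study cannot be settled without the protocol. What can be said is that the SAP as worded provides for it, and that sections 3.6, 3.7 and 6.1.2 need to be reconciled.

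**What to change.** Separate the two events in section 3.6, for example: *Recruitment closes when the recruitment target is met or after 24 months, whichever is sooner; the study ends when the last recruited participant has completed 30-day follow-up, died or withdrawn.* Keep 90 as the stated aim. It should not become a hard cap, because defibrillators are the randomised units (section 3.2) and a total of 90 does not secure 30 patients in each arm. Align the sentence with the protocol.

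If the closing date cannot move, count patients cut off by closure on their own line in the section 7 tables, apart from other missing values, so that the completeness of 30-day mRS can be read with and without them.

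The cost is at most about 30 more days of follow-up, plus a protocol amendment if the protocol carries the same rule. The alternative costs one extra row in the tables concerned.

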## 3.7 Timing of outcome assessments

	Cardiac arrest	Hospital	Day 30
Inclusion/exclusion criteria	✓	X	Х
Cardiac arrest data	✓	х	х
Patient identifiers	✓	✓	Х

			THE UNIVER
Adverse event reporting	✓	✓	х
National data opt- out check	,	(	х
Survival checks	√	√	х
Survival status	√	√	√
Hospital stay data	X	√	Х
Notification of enrolment and invitation to take part in follow up	х	√	х
Informed consent	Х	√	х
Neurological outcome (mRS)	x	x	✓

#### 4. STATISTICAL PRINCIPLES

#### 4.1 Confidence intervals and P values

There will not be a formal statistical analysis as the study has not been powered to assess difference in interventions. The analyses will be based on summary statistics, namely mean, standard deviation, median, interquartile ranges and missingness in the data. Where possible 95% confidence intervals will also be given.

#### 4.2 Adherence and protocol deviations

From Gamble, JAMA 2017;318(23) supplementary info: "A protocol deviation is defined as a failure to adhere to the protocol such as the wrong intervention being administered, incorrect data being collected and documented, errors in applying inclusion/exclusion criteria or missed follow-up visits."

## 4.2.1 Delivery of intervention

Adherence to the intervention will have been achieved when shocks have been delivered according to the allocated energy level. Patients may need one or more shocks. The protocol determines first, second and subsequent shock energies. It is possible that a protocol deviation may occur when delivering any or all shocks.

Treatment adherence rate will be assessed in terms of how many patients received the allocated first shock energy and, where more than one shock was delivered, how many received the correct subsequent shock energies. These will be reported as one of the secondary feasibility outcomes in the study report.

Short term post-shock outcomes (post-shock rhythms and return of spontaneous circulation (ROSC)) for only the first (up to) three shocks are being reported. Protocolised shock energies must be delivered for these shocks in order to be considered adherent. Where any energies deviate from the protocolised shock energies, this will be considered as non-compliant. Treatment adherence for each of the first three shocks will be reported via a table in the study report.

#### 4.2.2 Data collection and documentation

Where errors in data collection and documentation are identified, these will be rectified where possible. Where these cannot be rectified, data will be reported as missing and displayed in the data tables of the study report.

## 4.2.3 Eligibility errors

Data will not be collected for ineligible patients. Any data collected relating to a patient who is subsequently deemed ineligible will be deleted.

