# 4.2.4 Missed follow up visits

The proportion of missed follow up visits will be reported in the data tables in the study report.

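### SAP section 4.2.3 deletes all data on patients later found ineligible, with no provision to keep a count of them or any serious adverse event (SAE) they had

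*SAP*

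**What the plan says.** Section 4.2 adopts a definition of protocol deviation with four kinds: wrong intervention, incorrect data, and "errors in applying inclusion/exclusion criteria or missed follow-up visits". Sections 4.2.1 to 4.2.4 then take them in turn.

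- Wrong intervention (4.2.1): "Treatment adherence for each of the first three shocks will be reported via a table in the study report".
- Incorrect data (4.2.2): corrected where possible; otherwise "Where these cannot be rectified, data will be reported as missing and displayed in the data tables of the study report".
- Eligibility errors (4.2.3): no data are collected on ineligible patients, and "Any data collected relating to a patient who is subsequently deemed ineligible will be deleted".
- Missed visits (4.2.4): "The proportion of missed follow up visits will be reported in the data tables in the study report".

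Section 6.5 promises a summary of each SAE, covering severity, expectedness and causality, and excludes no group of patients. Both analysis populations in 4.3 are limited to eligible patients. The Withdrawals template in section 7 counts patients eligible, recruited, randomised, withdrawn and lost to follow-up.

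**The concern.** Three of the four kinds of deviation lead to something shown in the report. Eligibility errors lead only to deletion. This is an explicit rule, not a silence that the protocol might be expected to fill, and it sits badly with two other parts of the same document: the definition in 4.2 and the harms commitment in 6.5.

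Two things are at stake. The first is safety reporting. A patient who received a shock from a study device and had an SAE could drop out of the harms summary because an eligibility error was found later. The second is feasibility information. The SAP says the study is meant to inform a main trial, and how often a randomised device is used on a patient who turns out to be ineligible is something the designers of that trial would want to know. Without a count by arm, nobody can check whether such removals fell evenly across the three groups.

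**Working it through.** **Plan's own figure.** The only sample-size figure is the target of 90 in section 3.3: 3 arms × 30 patients = 90. It reproduces and is not in dispute. The point rests on reading sections together.

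**Step 1: can a treated patient later prove ineligible?** Yes. The defibrillator is the unit of randomisation (3.2), and section 5.4 notes that the intervention is delivered while the patient is unconscious. Section 4.2.3 itself foresees ineligibility being found after data have been collected. Section 5.2 gives two routes: the patient is found to be under 18, or an inclusion criterion is judged not to have been met.

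**Step 2: what happens to each kind of deviation?**

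| Kind (4.2) | Handling | Seen in the report? |
|---|---|---|
| Wrong intervention | Adherence table (4.2.1, section 7) | Yes |
| Incorrect data that cannot be corrected | Shown as missing (4.2.2) | Yes, within Missing |
| Eligibility error | Data deleted (4.2.3) | No provision stated |
| Missed visit | Proportion reported (4.2.4) | Yes |

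So two kinds are reported directly, one is merged with other missing values, and one has its data deleted with no stated report.

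**Step 3: does another section pick these patients up?** The populations in 4.3 cannot, because both require eligibility. The Withdrawals template has no row for patients found ineligible after enrolment. Section 5.4 asks for the timing of and reasons for withdrawal, but sets no matching requirement for removal on grounds of eligibility.

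**Step 4: 4.2.3 against 6.5.** For a treated patient who has an SAE and is later deemed ineligible, 4.2.3 removes any data and 6.5 requires summary data. Read literally, the two cannot both be followed.

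**Step 5: illustration of size.** The SAP gives no rate, so the number k of such patients is an assumption. With 90 eligible patients retained, the error rate is k/(90 + k). The exact (Clopper-Pearson) 95% limits with n = 90 + k are the 2.5% point of Beta(k, n − k + 1) and the 97.5% point of Beta(k + 1, n − k).

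| k (assumed) | Rate if a count is kept | 95% CI |
|---|---|---|
| 1 | 1/91 = 1.1% | 0.0 to 6.0 |
| 3 | 3/93 = 3.2% | 0.7 to 9.1 |
| 5 | 5/95 = 5.3% | 1.7 to 11.9 |
| 9 | 9/99 = 9.1% | 4.2 to 16.6 |

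If no count is kept anywhere, the retained data hold the same 90 patients in every row. Someone who took the absence of such cases to mean that none occurred would compute 0/90, with a 95% CI of 0 to 4.0%. The rates for k = 5 and k = 9 both lie above that upper limit.

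**The case against.** Several points on the other side are good, and most of them limit the concern.

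- **A count may exist elsewhere.** The rule deletes patient data; it does not forbid a log or a bare tally. The study flow diagram (5.3) is not visible in the text at hand, and the SAP lists SOPs on safety reporting and on deviations to be read alongside it. This stands. It is why the point is that the SAP makes no provision, not that reporting is impossible. A reader might infer that the report must show zero eligibility errors; the document does not say so.
- **Deletion may be required.** Consent comes after treatment, and a national data opt-out check is scheduled (3.7). Removal could be a condition of approval set out in the protocol. This stands too, and the fix allows for it.
- **The primary outcome is safe.** The objective rests on "establishing the number of eligible patients and the number recruited", and the outcome is the proportion of eligible patients randomised (6.1.1). An ineligible patient belongs in neither part of that proportion, so removal leaves it correct. A reader might infer otherwise, without support.
- **Patients are screened.** Eligibility is checked at the cardiac arrest (3.7) and screening data are reported (5.1). It would be wrong to say there is no individual screening.
- **Data errors are not erased.** A reader might infer that 4.2.2 wipes out a second kind of deviation. It does not: these values stay visible as missing. The related objective, "Identify the best outcome measures in terms of ease and reliability of recording by reviewing data completeness", is to be judged by completeness, and counting an unusable value as not obtained is a reasonable choice. Dividing the Missing row is optional, not the repair of an error.
- **Arm imbalance is a small worry.** Being under 18 is fixed before any shock and cannot depend on shock energy, and the study tests no hypotheses (3.4). That is fair for age. Whether an inclusion criterion was met can be more of a judgement, and 4.2.3 does not say who makes it.

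None of this reconciles 4.2.3 with 4.2 or 6.5 on the page.

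**Conclusion.** The point holds in a limited form. Section 4.2.3 orders deletion without exception. That leaves one of the four kinds of deviation with no stated report and conflicts with the promise in 6.5 for any treated patient later found ineligible. These conflicts are textual and need no assumed rate.

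The practical size is unknown. The range of 1.1% to 9.1% follows from assumed counts of 1 to 9 beside 90 retained patients; nothing in the SAP says which count is likely, or that any will occur. The planned primary proportion and the target of 90 are unaffected. The conclusion assumes that neither the flow diagram, nor the SOPs, nor the protocol already provides the count and the SAE rule; if they do, a cross-reference in 4.2.3 would be enough. It is a clarification worth making before analysis, chiefly for safety reporting and for what the main trial can learn.

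**What to change.** Amend 4.2.3 along these lines: identifiable and clinical data of a patient found ineligible after enrolment may be removed, but a non-identifying count is kept by allocated arm, reason and time of discovery. Any SAE in such a patient is recorded and reported under 6.5 before deletion. Show the count in the study flow diagram, and add a row for it to the Withdrawals template in section 7. Add a sentence to 6.5 saying that SAEs in these patients are included.

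The cost is a few sentences, a tally sheet and one table row. The small downside is that an anonymised tally must be retained, subject to any ethics or data-protection condition in the protocol; with small numbers, reasons should be grouped so that nobody can be identified.
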